## ABBREVIATIONS

AE	Adverse Event
CTRC	Cancer Therapy and Research Center
DSM	Data Safety Monitoring
DSMC	Data Safety Monitoring Committee
DSMP	Data Safety and Monitoring Plan
DSO	Data and Safety Officer
DQA	Director of Quality Assurance
EPCA	Early prostate cancer antigen
IRB	Institutional Review Board
QAD	Quality Assurance Division
PALS	Priority of Audit Level Score
PCa	Prostate Cancer
PI	Principal Investigator
PSA	Prostate-specific antigen
PSMA	Prostate-specific membrane antigen
SAE	Serious Adverse Event
UPIRSO	Unanticipated Problem Involving Risks to Subjects or Others
uPA	Urokinase plasminogen activator
uPAR	Urokinase plasminogen activator receptor
UTHSCSA	University of Texas Health Science Center at San Antonio

## 1.0 INTRODUCTION AND RATIONALE

Several reports suggest that physical activity after cancer diagnosis is associated with better cancer-specific and overall survival in individuals diagnosed with PCa. The role of a healthy diet and sufficient physical activity in cancer prevention have been well documented, and it is widely accepted that a lack of exercise can increase an individual's risk of recurrence or developing new cancers. Increasing attention is now being given to the role of lifestyle in cancer survivorship. There is a growing body of evidence for lifestyle interventions that aim to promote physical activity as having the potential to counter some of the adverse effects of cancer treatments, disease progression and other health outcomes. Exercise performed 2-3 times a week has been shown to improve physical fitness, functional performance, and quality of life in men with PCa; however, few men with PCa exercise regularly and do not meet national physical activity guidelines. A potential explanation on the lack of exercise in men with PCa is the absence of a structured, home-based, exercise program. While studies have shown positive effects of exercise in men with PCa, little is known about how physical activity effects tumor physiology in men with PCa. The primary objective of this pilot study is to gather preliminary data regarding the impact of a novel, home-based exercise program on PCa biomarkers associated with recurrence and metastasis of PCa in men under active surveillance.

**1.1 Prognostic Biomarkers for PCa Recurrence.** Over the years, many biomarkers have been used for the diagnosis and follow-up of PCa. **PSA** (prostate specific antigen) is the most common marker used, however, recently PSA screening has fallen under controversy based on the high number of false positive diagnosis for PCa. Out of men that display elevated PSA levels in blood, only 25% are associated with PCa. Therefore, other biomarkers need to be studied to more accurately determine the impact of exercise on disease progression. **PSMA**, **EPCA**, **uPA** and **uPAR** are promising PCa markers shed by the tumor that represent the advancement or regression of the prostate tumor that can be quantified in blood. Prostate-specific membrane antigen (**PSMA**) is a type II integral membrane glycoprotein that is overexpressed in the epithelial cells of PCa patients. Literature supports its role in measuring progression of PCa post treatment based on its 94.5% specificity to PCa from other types of malignancy. Early prostate cancer antigen (**EPCA**) is a prostate cancer-associated nuclear structural protein displaying sensitivity and specificity for prostate cancer. In a recent study, EPCA was found to be significantly elevated in localized PCa and strongly predicted cancer progression. Urokinase plasminogen activator (**uPA**) and its receptor (**uPAR**) have been connected with PCa stage and bone metastases. Preoperative plasma uPA was a strong predictor of biochemical recurrence. Elevated levels of both preoperative uPA and uPAR were associated with aggressive biochemical recurrence including development of distant metastasis, suggesting an association with occult metastatic disease. The uPA axis is involved in various phases of tumor development and can be used as a biomarker to determine the effectiveness of exercise in modulating tumor progression. Circulating tumor cells (CTCs) can be quantified through microfiltration and as indicative of advanced prostate cancer and can be an alternative source for disease profiling and

prognostication. While tumor biopsies following an exercise intervention fall outside the scope of current practices in PCa treatment, these biomarkers have the potential to act as circulating biopsy of the tumor.

**1.2 Biomarker for Cancer-related Fatigue.** Prostate cancer survivors commonly report having 1 or more cancer related symptom that impacts their quality of life. One common symptom associated with cancer, termed cancer-related fatigue, is exceedingly common and treatable not only in prostate cancer patients but other cancers as well. Cancer-related fatigue is reported by 50-90% of patients as a symptom of their cancer [4]. Patients report fatigue as one of the most important and distressing symptoms related to cancer and its treatment and is a strong predictor of clinical patient satisfaction as well as patient quality of life. Measurement of fatigue in PCa has typically come in the form of paper-based surveys. Opportunities exist for advancing the field with novel methods of assessing fatigue in this clinical population. Biomarkers would provide an objective method to track a patient's fatigue level during treatment, allowing clinicians to optimize treatment with respect to the patient's fatigue level. In previous studies, our collaborators at Hyperion Biotechnology identified a salivary biomarker of physical fatigue, called the Fatigue Biomarker Index (FBI) and demonstrated the utility of this marker in predicting the outcome of physically demanding military training. Using a similar approach to biomarker discovery, the same collaborators have also identified a salivary biomarker candidate for chronic fatigue syndrome. Both of these salivary biomarkers are based on changes in levels of naturally occurring peptide fragments arising from the same family of salivary proteins, the salivary Proline –rich Proteins (PRPs). Others have also identified changes in the levels of similar salivary peptides in Sjogren's syndrome, a disease associated with significant fatigue. Taken together, these finds suggest a fundamental physiological link between a person's fatigue level and the composition of the individual's saliva. Investigating whether similar changes in saliva are associated with fatigue is justified.

**1.3 Survey measurements for quality of life.** Quality of life will be measured using the Short-Form-36 and the Functional Assessment of Chronic Illness Therapy-Fatigue surveys.

Health-Related Quality of Life (SF-36) is designed to assess the health status of patients and has been used previously in this population. The SF-36 assesses eight components of quality of life (physical functioning, role functioning, bodily pain, general health, vitality, social functioning, mental health, and emotional health) that is evidence generated with well-established reliability and validity to support its use.

Functional Assessment of Chronic Illness Therapy-Fatigue (FACIT-F) is a self-reported survey evaluating the impact of fatigue in the patient population. The FACIT-F is a 13 item survey rated on a 5 point scale deemed reliable and valid in measuring fatigue.

**1.4 Rationale for this trial design.** This first of its kind study intends to collect preliminary data on the impact of a home-based exercise program that can improve prognosis, physical function and quality of life in men with PCa; the results of which have the potential to promote health restoration and wellness while reducing cancer

progression in men with PCa. This study will provide data on the feasibility in conducting a home based exercise study and pilot data on the impact of exercise on circulating concentrations of biomarkers reported in the literature to be beneficial for the prognostication of prostate cancer and salivary biomarker for fatigue.

## **2.0 STUDY OBJECTIVES**

**2.1 Primary Objective:** To demonstrate the impact of a home based exercise program versus wait-list control to modulate circulating prognostic biomarkers PSA, PSMA, EPCA, uPA and uPAR in men with prostate cancer under active surveillance..

2.1.1 Hypothesis: The home based exercise program participants will have significantly lower concentrations of circulating biomarkers compared to their non-exercising counterparts.

**2.2 Secondary Objective:** To determine the impact of a home based exercise program versus wait-list control to modulate a novel salivary biomarker for fatigue in men with prostate cancer under active surveillance.

### **2.3 Other Objective:**

2.3.1 To demonstrate the capability of a home based exercise program versus wait-list control in improving physical function (as measured by the 6 minute walk) and body composition in men with prostate cancer under active surveillance.

2.3.1.1 Hypothesis: The exercise group will have significant improvements in the physical function measure and body composition compared to the wait-list control group

2.3.2 To demonstrate the feasibility of conducting a home based exercise investigation.

2.3.2.1 Hypothesis: Based on the simplicity of this program, we believe that we will be able to achieve our desired recruitment and retention needs to complete the objectives of this study.

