## **4.0 SELECTION OF PATIENT**

### **4.1 Number of patients planned**

This study plans to enroll 30 men with prostate cancer under active surveillance with 15 men in each arm.

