## **5.0 DESCRIPTION OF INTERVENTION**

**5.1 Home-based exercise program.** The intervention will include a combination of both aerobic and body-weight based exercises. The aerobic portion of the intervention will include 5 days of light to moderate intensity walking for 30 mins (weekly total of 150 mins). Intensity will be set at 40-60% of the individual's heart rate reserve using the Karvonen formula (Exercise HR = % of target intensity ( $HR_{max} - HR_{rest}$ ) +  $HR_{rest}$ ). Participants

will be given their targeted HR range by the PI and will be taught how to palpate and calculate HR prior to the beginning of the program. The body-weight based exercises will be done 3 times a week. Exercises will consist of 3 sets of 15 reps of bodyweight squats, incline push-ups, and hip thrusts. If these exercises cannot be performed, lower intensity exercises such as sit-to-stand, wall push up and pelvic tilt can be replaced. These exercises are aimed at increasing strength and endurance of the major muscle groups of the body. Individuals in this group will be given a pocket guide with instructions on how to safely perform the exercises and document the completion of the exercises.

**5.2 Waitlist-Control Group.** Participants assigned to this group will be asked to maintain normal activity and visit the CTRC fitness center for research appointments.

**5.3 Method of assigning patients to intervention group.** Patients eligible to participate in this study will be allocated to either the exercise group or wait-list control group (1:1) based on a pre-specified randomization list

Example:

**Set #1:** 2, 1, 2, 2, 1, 2, 2, 2, 1, 1, 2, 2, 2, 1, 2, 1, 2, 2, 2, 1, 1, 1, 1, 2, 2, 1, 2, 1, 2, 2

1: Control Group; 2: Intervention Group

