## 7.0 STUDY PROCEDURES

### 7.1 Visit schedule

Patients will be asked to attend 4 visit with the study investigators. Description of each visit is detailed below.

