### 7.3 Description by type of visit

7.3.1 Visit 1 (Baseline Visit) – This will be the first visit in this study and should last about 30-45 minutes. At this session, we will review the consent form, explain the purpose and procedures of the study, ask the subject to sign the consent form if you agree to participate in the study, and randomly assign the subject to one of the two groups mentioned above. Following this, the following things will happen:

1. Assignment of a Nike FitBit – Each participant, no matter which study arm, will be provided with a Nike Fitbit during the 6 month program. The FitBit will monitor activity and will assist the research team in tracking activity and sleep habits. We will instruct subjects on the use and care of the FitBit.
2. Blood Draw –15 mL of blood (two tubes or 1 tablespoon or 3 teaspoons) to measure circulating markers (PSA, PSMA, EPCA, uPA and uPAR) and circulating tumor cells.
3. Saliva Collection – we will collect about 4 mL of saliva (1/4 of a tablespoon or 3/4 teaspoon) to measure FBI concentrations in saliva.
4. Surveys for Quality of Life and Fatigue – subjects will be asked to complete 2 surveys that will take about 5 minutes to complete. These surveys are:
  - a. Health-Related Quality of Life (SF-36) – this survey will assess subject's overall health status, including physical functioning, role functioning, bodily pain, general health, vitality, social functioning, mental health and emotional health.
  - b. Functional Assessment of Chronic Illness – Fatigue (FACIT-F) – This survey evaluates the impact of fatigue in men with prostate cancer.

5. Body Composition, Body Mass Index and Body Density – will measure body fat percentage by measuring skinfold thickness at 3 sites (chest, abdomen, thigh). Body density will be measured using body fat percentage plus the addition of waist and arm circumference. Body mass index will be calculated by collecting by height and weight measurements from the subjects.
6. 6 minute walk test –overall physical function will be measured using the 6 minute walk test. We will track the distance traveled and use this as baseline score.

7.3.2 Visit 2 and Visit 3 (12 week and 18 week visit) – the following activities will be done at the 12 week and 18 week visit:

1. Blood Draw – we will collect 10 mL (2 teaspoons) to measure circulating markers (PSA, PSMA, EPCA, uPA and uPAR). Note: This is different than at baseline and final visit to quantify circulating tumor cells.

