2. Download FitBit Data – subjects will be asked to bring the FitBit to this visit so we can download the data that is on the FitBit.
3. Saliva Collection – we will collect about 4 mL of saliva (1/4 of a tablespoon or ¾ teaspoon) to measure FBI concentrations in saliva
4. Body Composition, Body Mass Index and Body Density – will measure body fat percentage by measuring skinfold thickness at 3 sites (chest, abdomen, thigh). We will also measure body mass index by collecting height and weight. Body density will be measured using body fat percentage plus the addition of waist and arm circumference.

7.3.3 Visit 4 (24 week visit; End of Study Visit) – the following activities will be done at the 24 weeks visit (or end of study visit)

1. Blood Draw – we will collect 15 mL of blood (two tubes or 1 tablespoon or 3 teaspoons) to measure circulating markers (PSA, PSMA, EPCA, uPA and uPAR) and circulating tumor cells.
2. Saliva Collection – we will collect about 4 mL of saliva (1/4 of a tablespoon or ¾ teaspoon) to measure FBI concentrations in saliva

3. Surveys for Quality of Life and Fatigue – subjects will be asked to complete 2 surveys that will take about 5 minutes to complete. These surveys are:
  - a. Health-Related Quality of Life (SF-36) – this survey will assess subject's overall health status, including physical functioning, role functioning, bodily pain, general health, vitality, social functioning, mental health and emotional health.
  - b. Functional Assessment of Chronic Illness – Fatigue (FACIT-F) – This survey evaluates the impact of fatigue in men with prostate cancer.
4. Body Composition, Body Mass Index and Body Density – will measure body fat percentage by measuring skinfold thickness at 3 sites (chest, abdomen, thigh). We will also measure body mass index by collecting height and weight. Body density will be measured using body fat percentage plus the addition of waist and arm circumference.
5. 6 minute walk test – we measure overall physical function by asking subjects to walk for 6 minutes. We will track the distance traveled and use this as the post-intervention score.
6. Return Nike FitBit – subjects will be asked to return the Nike FitBit to the research team. Data from the FitBit will be downloaded. After downloading, all data that is on the FitBit will be erased. A summary of the subject's activity can be provided if desired.

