## **8.0 STATISTICAL CONSIDERATIONS**

### **8.1 Statistical analysis plan**

Analysis will be done after all participants have completed the 12-week and 24-week timepoints, respectively. The interim analysis at 12-weeks will be for safety and efficacy of the intervention and will include a between group comparison of circulating biomarkers and a review of adverse events reported by study participants.

Statistical analysis will be performed using IBM SPSS 19.0 software. A 2 group analysis of variance (ANOVA) will be used to compare changes in biomarkers, physical function, body composition, body density, and quality of life between the exercise group and the WLC. Pearson's Product Moment Correlation will be used to measure associations between biomarkers in Aim 1 to body composition, body density, physical function and quality of life measured in aim 2. A value of  $p < 0.05$  will be considered statistically significant. The results of this study will be used to calculate power and determine sample size for future research questions in this field.

We will also evaluate the projects procedures and timeline for feasibility. We will document and review our timelines for recruitment for this pilot and ask participants to comment on their experiences in this project with pointed efforts to understand ways to improve the project procedures for effectiveness and efficiency. We will also assess feasibility by documenting and reviewing study patient description described below.

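### No masked or separate assessor is specified for the skinfolds and 6-minute walk under objective 2.3.1, so observer bias could inflate the false-positive risk and could not be told apart from an exercise effect

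*Combined protocol and SAP*

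**What the plan says.** Section 2.3.1 sets out to show benefit in "improving physical function (as measured by the 6 minute walk) and body composition in men with prostate cancer under active surveillance", and hypothesis 2.3.1.1 predicts significant improvement over control in both. Section 8.1 compares changes between arms by a two-group ANOVA: "A value of $p < 0.05$ will be considered statistically significant".

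On who does what:

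- Section 7.1: "Patients will be asked to attend 4 visit with the study investigators".
- Section 7.3.1: at Visit 1 the team will "randomly assign the subject to one of the two groups mentioned above". The baseline skinfolds and walk are listed after that step.
- Section 5.1: participants "will be given their targeted HR range by the PI and will be taught how to palpate and calculate HR".
- Section 7.3.2: skinfolds are taken at weeks 12 and 18. The FitBit download is item 2 on the list and body composition is item 4.
- Section 7.3.3: at week 24 skinfolds are repeated and "we measure overall physical function by asking subjects to walk for 6 minutes". Here the FitBit download comes last.

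The design statement in 3.1 and the visit descriptions in 7.3 mention no masking, no independent assessor and no standard script for the walk.

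**The concern.** Walk distance responds to the encouragement given. A skinfold reading depends on where and how the caliper is placed. If the person measuring knows the arm, small and quite unconscious differences in either can favour the exercise group. Seeing the activity data just before the caliper reading at Visits 2 and 3 would add to that knowledge.

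Such a difference enters the estimate directly: the expected between-arm difference in change equals the true effect plus the bias. More precise measurement or a different model would not remove it, because it is aligned with the arm. The estimate moves whether or not p falls below 0.05. Section 8.1 intends to use the results to size later research, so a biased effect on function or body composition could carry forward. Section 8.1 also correlates the biomarkers with these same measures.

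**Working it through.** **Inputs from the plan.** Sample size (4.1): "This study plans to enroll 30 men with prostate cancer under active surveillance with 15 men in each arm". Allocation 1:1 (5.3). Threshold 0.05 (8.1); sidedness is not stated, so two-sided is assumed. A two-group ANOVA on change is equivalent to a two-sample t test, with 15 + 15 − 2 = 28 df.

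**Inputs the plan does not give.** It has no SD, effect size, power calculation or size of observer bias, so it offers no figure to reproduce. Bias b is therefore expressed in SDs of the change score, and every value of b is an assumption.

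**Step 1: difference needed for significance.** The standard error of the difference is √(2/15) = 0.365 SD. The critical t at 28 df is 2.048. The observed difference must reach 2.048 × 0.365 = 0.75 SD.

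**Step 2: one outcome, no true effect.** Under bias b, the t statistic is noncentral with noncentrality b/√(2/15) = 2.739b. The chance of a falsely favourable result is P(T > 2.048).

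| b (SD) | Noncentrality | Favourable p<0.05 | Either direction |
|---|---|---|---|
| 0 | 0 | 2.5% | 5.0% |
| 0.2 | 0.55 | 7.6% | 8.3% |
| 0.25 | 0.68 | 9.7% | 10.1% |
| 0.3 | 0.82 | 12.2% | 12.5% |
| 0.5 | 1.37 | 26.2% | 26.2% |
| 0.75 | 2.05 | 50.9% | 50.9% |

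The favourable column is the relevant one, because the hypothesis is improvement. A bias of 0.2 SD multiplies the nominal 2.5% by about 3 (7.6/2.5), and 0.3 SD by about 5 (12.2/2.5).

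**Step 3: both outcomes equally biased.** This comes from a simulation of 50,000 trials, with correlation between the outcomes from 0 to 0.6.

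| b (SD) | At least one favourable | Both favourable |
|---|---|---|
| 0.2 | 12–15% | 1–3% |
| 0.3 | 19–23% | 1–5% |
| 0.5 | 38–46% | 7–14% |

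**Step 4: in natural units, with assumed SDs.** Favourable result only.

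- Walk, SD of change 50 m (range 40 to 60): significance needs 37 m (30 to 45). A 10 m bias gives 7.6% (9.7% at SD 40, 6.4% at SD 60). A 20 m bias gives 18.4% (26.2% and 14.0%).
- Body fat, SD of change 2 points (range 1.5 to 2.5): a 0.5-point bias is 0.25 SD and gives 9.7% (14.0% at SD 1.5, 7.6% at SD 2.5). A 1-point bias is 0.5 SD and gives 26.2% (42.2% and 18.4%).

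**Step 5: sensitivity to numbers per arm.** Section 6.0 does not replace men who discontinue. With 12 per arm (assumed), the threshold rises to 0.85 SD and the rates at 0.2, 0.25 and 0.5 SD become 6.8%, 8.5% and 21.5%. With 12 control and 18 intervention, as in the example list in 5.3, they are 7.5%, 9.5% and 25.3%. Neither case changes the picture.

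**The case against.** The strongest arguments on the other side are the following.

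- **The bias sizes are invented.** They are: the documents support no particular value. The table shows how risk responds to bias and does not estimate the bias in this trial.
- **Modest bias does not by itself produce the hypothesised result.** A reader might infer that it would. The figures do not bear this out. At 0.2 to 0.25 SD more than 90% of trials show no falsely favourable result on a given outcome, and even odds need about 0.75 SD. Hypothesis 2.3.1.1 names both measures, and a false positive on both at 0.2 SD occurs only 1–3% of the time. What stands is inflation of the risk.
- **The text does not say that one person assigns, coaches and measures.** A reader might infer it from the repeated 'we'. That wording is lay and is no staffing roster, the skinfold items name no measurer, the allocation list is fixed in advance, and 9.1.3 mentions a research assistant. The documents support only that no separation or masking is specified.
- **The men cannot be masked.** This is true, and their own effort on the walk would remain a source of bias. It does not excuse leaving the observer's part uncontrolled.
- **This is an 'other' objective in a 30-man pilot.** This is also true, and it limits the weight of the point. Even so, the plan attaches a significance test and a directional hypothesis to these outcomes.

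**Conclusion.** The gap is real. For the two observer-dependent outcomes of objective 2.3.1, the protocol names no masked or separate assessor, while the team running the visits also assigns the arm. Because baseline measures are listed after assignment and the analysis is of change, Visit 1 is exposed as well as follow-up.

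Any observer bias would shift the estimated effect by its full size and could not be separated from an exercise effect. At 15 per arm, a falsely favourable result per outcome would rise from 2.5% to about 8%, 10% and 26% under assumed bias of 0.2, 0.25 and 0.5 SD. These rates assume no true effect, normal changes, a two-sided 0.05 test and complete data.

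A reader might go further and call the 2.3.1 results uninterpretable, or doubt the trial's main conclusion. The documents support neither. Bias would weaken these estimates without voiding them, and the primary blood markers and secondary salivary marker are laboratory-measured and largely untouched. The point is minor to moderate, and worth acting on because later analysis cannot repair it.

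**What to change.** In 7.3.2 and 7.3.3, add that:

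- the walk follows a fixed script;
- skinfolds, circumferences and the walk are done before the FitBit download and before any discussion of exercise;
- the measurer does not see the man's earlier values;
- where existing staffing allows, the measurer is a team member who neither assigned the arm nor taught the programme and is not told the arm, with the same measurer for a given man at every visit including baseline, so that between-rater skinfold error is not added;
- the measurer records whether he or she became aware of the arm.

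In 7.3.1, take the Visit 1 skinfolds and walk before the arm is assigned.

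If nobody on the team can be kept unaware of the arm, keep the script, the order and the hidden values, and report the 2.3.1 results as unmasked.

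The cost is protocol wording, a changed order of tasks and some rostering. Sample size, visits and analysis are unchanged. The documents give no staffing numbers, so they do not show that an unaware measurer is available, which is why that step is conditional. Masking will be imperfect because men may reveal their arm, and their own effort on the walk and the self-report surveys stay unmasked.
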